3.0 LIST OF ACRONYMS, ABBREVIATIONS AND DEFINITIONS OF TERMS

Abbreviation	Definition
AE	Adverse event
ANCOVA	Analysis of covariance
Anti-interleukin-10 antibody	Antibody that binds IL-10
aPTT	Activated partial thromboplastin time
BPI	Brief Pain Inventory of Intensity and Interference
BMI	Body mass index
CBC	Complete blood count
CTCAE	Common Terminology Criteria for Adverse Events (V5.0)
CCI	Chronic Constriction Injury-induced pain model
CNS	Central nervous system
CRF	Case report form
ds DNA	Double stranded DNA
FDA	Food and Drug Administration
FU	Follow-up
GCP	Good Clinical Practice
GLP	Good Laboratory Practice
HREC	Human Research Ethics Committee
IA	Intra-articular
IB	Investigator's Brochure
ICF	Informed consent form
ICH	International Council for Harmonisation
IEC	Independent Ethics Committee
IL	Interleukin
IL-10	Interleukin-10
Index Knee	The knee receiving injection of study drug
INR	International normalized ratio

Abbreviation	Definition
IRB	Institutional Review Board
IT	Intrathecal
ITT	Intent-to-Treat
IV	Intravenous
KOOS	Knee injury and Osteoarthritis Outcome Score
MedDRA	Medical Dictionary for Regulatory Activities
NP	Neuropathic
OA	Osteoarthritis
OTC	Over the counter
pDNA	Plasmid DNA
PI	Principal Investigator
PT	Prothrombin time
PTT	Partial thromboplastin time
QST	Quantitative Sensory Testing
SAE	Serious adverse event
SAER	Serious adverse event report
SAP	Statistical Analysis Plan
SOP	Standard operating procedure
TEAE	Treatment-emergent adverse event
TGA	Therapeutics Goods Administration
VASPI or VAS	Visual Analog Scale of Pain Intensity
VNRS	Verbal Numerical Rating Scale
WOMAC	Western Ontario and McMaster Universities Osteoarthritis Index
XT-150	Plasmid DNA, proprietary variant of human IL-10 protein, formulated in a solution for injection.

4.0 BACKGROUND AND RATIONALE

4.1 XT-150

Complete and current information on XT-150 can be found in the Investigator's Brochure (IB) version 7, 24 May 2019.

XT-150 is a new treatment for chronic pain from pathogenic inflammation. It is a plasmid designed to transiently express a variant of the anti-inflammatory cytokine, interleukin-10 (IL-10).

The mechanism of action of XT-150 is through a reduction in inflammation. XT-150 returns target tissues to normal function by induction and release of a single-amino acid variant human IL-10 (a human anti-inflammatory cytokine, IL-10var), that acts to modulate inflammation through multiple pathways: Suppressing pro-inflammatory cytokine production and release, down-regulating cytokine receptors and up-regulating antagonists; and inhibiting hydrogen peroxide and nitric oxide production (Moore 2001; Sawada 2001).

When XT-150 is administered by injection at the site of chronic inflammation, low levels of human IL-10var protein are produced over the following weeks, which reduces the pain associated with joint inflammation.

Additionally, the targeted delivery of XT-150 directly to the joint knee space restricts the potential for systemic AEs.

XT-150 presents a treatment opportunity for patients suffering significant damage from osteoarthritis, such as those in need of knee replacement; or the many patients who are not good surgical candidates for knee replacement. This study will help select doses to establish safety, tolerability, and effectiveness in subsequent clinical trials.

4.2 Nonclinical Pharmacology and Toxicology

The IB provides detailed summaries of GLP and non-GLP preclinical pharmacology and toxicology studies.

4.3 Clinical Experience

Three clinical trials with XT-150 are complete or in progress. XT-150 has been safe and well tolerated after a single injection of up to 600 μg (the highest dose yet delivered) in 1-mL or 2-mL (600 μg) intra-articular knee injections. Study subjects have been followed for up to 6 months following the XT-150 injection. No Serious Adverse Events (SAEs) have been reported to date. The IB contains detailed summaries.

XT-150 is not marketed in any country.

Table 3. Human Clinical Trials with XT-150

Study	Design	Sites	Results Summary
XT-150-1-0201 NCT03282149 (completed March 30, 2019)	Sequential dose escalation (15, 150, and 450 µg) Placebo controlled (1:3) 8 subjects per cohort (6 active:2 placebo) Safety and Efficacy follow-up assessments for 6 months	University of Adelaide	No Serious Adverse Events Mild injection site reactions No changes in acute phase biomarkers or lab chemistries No induction of anti-drug antibodies

Study	Design	Sites	Results Summary
XT-150-1-0202 NCT03477487 (Completed July 12, 2019)	Sequential dose escalations (15, 150, 450 and 600 µg) Open label, non-comparator 8 subjects per group Safety and efficacy follow-up assessments for 6 months	Napa Pain Institute (Neurovations)	No Serious Adverse Events Mild injection site reactions No changes in acute phase biomarkers or lab chemistries
XT-150-1-0203 NCT03769662 (Completed Oct 30, 2019)	Single dose – 450 µg Open-label, non-comparator Up to 24 participants who completed the 0201 study • Placebo – first injection; or • Injection into 0201-untreated knee; or • Second injection of the 0201-treated knee Safety and efficacy follow-up assessments for 6 months Test for anti-IL-10 antibody following a second injection	University of Adelaide	16 of 24 participants from 0201 study received 450 μg XT-150 as of 1 May 2019. One unrelated SAE of a fall leading to hospitalization for a broken hip No XT-150-related AEs

4.4 Summary of Known Benefits and Potential Risks

4.4.1 Potential Benefits

Participants will receive active investigational product or phosphate-buffered saline injection (placebo). Potential therapeutic benefits of XT-150 for the treatment of OA pain are:

- Increased mobility for many weeks following a single dose of XT-150
- Reduction in requirement for pain medications and therapies

Reduction in pain symptoms for many weeks following a single dose of XT-150.

4.4.2 Known Risks

Intra-articular injection in the knee with XT-150 has been well tolerated in clinical trials of OA pain. Based on multiple animal studies and 3 clinical trials, XT-150-related adverse events are most commonly minor injection site reactions.

4.4.3 Potential Risks

Nonclinical studies and clinical studies with XT-150 are described in the IB. XT-150 posed minimal risk in these studies. General risks associated with IA injection are injection site reactions and infection, which will be explicitly captured in follow-up safety assessments.

4.4.3.1 Safety of DNA as a Therapeutic Agent

DNA as a therapeutic agent has been well tolerated. The main theoretical safety concerns regarding the clinical use of DNA are that they might integrate with the host/patient DNA, or that injection of foreign DNA might stimulate anti-DNA antibodies or an autoimmune reaction (Prazeres 2014).

With both DNA vaccines and DNA plasmids, the risk of integration was repeatedly found to be low with years of research into the possibility (FDA, 2005; Prazeres 2014). With plasmids, the potential for integration has been removed by excluding any sequences that might drive homologous recombination and integration into the genome. In fact, excluding these elements lowers the risk of plasmid integration to less than the rate of naturally occurring mutations (Prazeres 2014). XT-150 has been designed to transiently express a variant of human IL-10 without integrating into the genome.

Immunogenicity of DNA appears to be low (Ferraro 2011), and correlates to the lack of success of DNA agents (even pathogenic bacterial sequences) as vaccines. No link has been found between plasmid DNA injections and any clinical markers of autoimmunity (Prazeres 2014).

In addition, DNA plasmids have been used in research and development for 25 years. Synthetic vectors share the non-infectious properties of viral vectors, and elicit low immunogenicity and lower toxicity compared to viral vectors (Xu 2011; Gôrecki 2006).

4.4.4 Safety of Interleukin-10

Published studies in the literature have reported IL-10 protein therapy to be safe in humans. The safety of IL-10 protein injections was studied in healthy volunteers at doses up to $100 \,\mu\text{g/kg}$. Details of these studies can be found in the IB.

Protocol XT-150-2-0204

After injection in healthy volunteers at doses up to 100 μg/kg, wild-type human IL-10 protein was found to be rapidly degraded with a half-life of 2.0 to 4.5 hours (Chernoff 1995; Huhn 1996, 1997; Milligan 2005). In the Huhn (1997) study, after intravenous administration of high doses of IL-10 protein (100 μg/kg), 42% (15/36) of the volunteers experienced flu-like adverse effects, the most common of which were headache (11/36 participants, 31%), fever (5/36, 14%), and back pain (3/36, 8%). Pharmacodynamic effects from intravenous IL-10 treatment included transient increases in neutrophils and monocytes, and decreases in lymphocytes, which peaked around 6 hours after injection (Chernoff 1995). When given intravenously IL-10 was also found to inhibit production of the cytokines IL-1β and tumor necrosis factor-alpha (TNF-α), and reduce T-lymphocyte stimulation.

Recombinant human IL-10 has been clinically tested as a therapy in humans in a number of indications without serious or irreversible side effects. In these trials, IL-10 injections of up to 25 μg/kg were reported to be well tolerated. With chronic intravenous and high doses, statistically significant hematological changes were observed, as well as fever. Adverse events of neutrophilia, headache, injection site pain, anemia, and nausea were observed with daily dosages in patients with Crohn's Disease.

As an anti-inflammatory agent, the biological activity of IL-10 is different than that of other interleukins. Exogenous IL-10 is the only interleukin shown to be well tolerated. However, the anti-inflammatory activity of IL-10 treatment could mask latent infections (Moore 2001). Since IL-10 has been theorized to mask latent infections, any participant who has a current autoimmune condition or documented immunodeficiency, has a history of immunosuppression, or is currently receiving treatment with immunosuppressive agents is excluded from this study.

Note that XT-150 is a sterile aqueous formulation of a plasmid designed to transiently express a proprietary variant of IL-10. XT-150 expression of the variant IL-10 is expected to be safer than systemic injection of active IL-10 protein as therapy for the following reasons:

- Rather than injections of IL-10 protein, XT-150 treatment will result in IL-10 levels that exist transiently and at a much lower concentration.
- The IL-10 levels from XT-150 expression will be localized in the knee space. Low systemic levels of IL-10 from XT-150 treatment may be present for short periods of time and if present are unlikely to lead to adverse effects,

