7.0 SELECTION, DISCONTINUATION, AND WITHDRAWAL OF PARTICIPANTS

To be enrolled in this study, all participants must meet all of the following inclusion criteria and none of the exclusion criteria.

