7.2 Participant Exclusion Criteria

Participants must NOT meet any of the following exclusion criteria:

- 1. Hypersensitivity, allergy, or significant reaction to any ingredient of the study drug, including double-stranded DNA,
- 2. Previously received XT-150 injection(s)
- 3. Scheduled partial or complete knee replacement within 6 months; participant agrees not to schedule a knee replacement during Stage A of the study
- 4. History of knee arthroplasty on the Index Knee selected for study injection(s)
- 5. History of rheumatoid arthritis or other inflammatory disease
- 6. History of immunosuppressive therapy; systemic steroids in the last 3 months
- 7. Received knee injection with hyaluronic acid or stem-cells in the last 6 months
- 8. Knee injection of glucocorticoid in the last 3 months
- 9. Current treatment with systemic immunosuppressive (systemic corticosteroid therapy or other strong immunosuppressant)
- 10. Currently receiving systemic chemotherapy or radiation therapy for malignancy
- 11. Clinically significant hepatic disease as indicated by clinical laboratory results ≥3 times the upper limit of normal for any liver function test (e.g., aspartate aminotransferase, alanine aminotransferase)
- 12. Severe anemia (Grade 3; hemoglobin <8.0 g/dL, <4.9 mmol/L, <80 g/L; transfusion indicated), Grade 1 white cell counts (lymphocytes <LLN 800/mm³; <LLN 0.8 x 10⁹ /L, neutrophils <LLN 1500/mm³; <LLN 1.5 x 10⁹ /L)
- 13. Positive serology for human immunodeficiency virus, hepatitis B virus, or hepatitis C virus

- 14. Significant neuropsychiatric conditions; dementia, major depression, or altered mental state that in the opinion of the Investigator will interfere with study participation
- 15. Current treatment with systemic antibiotics or antivirals (EXCEPTION: topical treatments)
- 16. Current anticoagulant or anti-platelet treatment (e.g., warfarin, heparins, factor X inhibitors, clopidogrel, prasugrel, ticagrelor, or dipyridamole). Low-dose (≤ 325 mg/day) aspirin is permitted.
- 17. Known or suspected history of active alcohol or intravenous/oral drug abuse within 1 year before the screening visit
- 18. Use of any investigational drug or device within 3 months before enrollment or current participation in a trial that included intervention with a drug or device; or currently participating in an investigational drug or device study

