8.7.1 Prohibited medications

The following treatments are prohibited prior to study drug administration:

- Current treatment with antibiotics or antiviral agents, except as topical treatments.
- Current treatment with immunosuppressive agents
- Current treatment with anti-platelets or anticoagulants. Aspirin ≤325 mg/day is allowed
- Current use of systemic corticosteroids
- Alcohol or illicit drug abuse within 1 year before the screening visit

Concomitant medications for pain will be allowed at doses and frequencies prescribed prior to the study treatment. New medications or escalation of pre-study treatments will be captured on CRFs during the 360-day evaluation period.

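### Section 4.4.4 says participants with a current autoimmune condition or documented immunodeficiency are excluded, but the exclusion list names neither group and covers each only in part

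*Protocol*

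**What the plan says.** Protocol section 4.4.4 notes that the anti-inflammatory action of IL-10 could in theory hide a latent infection. As its response it lists four groups that may not take part. The first two are covered by "any participant who has a current autoimmune condition or documented immunodeficiency". The other two follow in the same sentence: anyone who "has a history of immunosuppression, or is currently receiving treatment with immunosuppressive agents is excluded from this study". The statement carries no qualification.

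Eligibility is applied through the numbered lists. Section 7.0 requires that "all participants must meet all of the following inclusion criteria and none of the exclusion criteria". Sections 9.1 (Screening), 9.2 (Baseline) and 9.3 (Day 0) each tell the site to check those criteria, and section 14.1 makes the investigator responsible for enrolling only participants who meet them.

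The relevant exclusions in section 7.2, repeated in the synopsis, are:
- Exclusion 5: "History of rheumatoid arthritis or other inflammatory disease".
- Exclusion 6: "History of immunosuppressive therapy; systemic steroids in the last 3 months".
- Exclusion 9: "Current treatment with systemic immunosuppressive (systemic corticosteroid therapy or other strong immunosuppressant").
- Exclusion 10: current systemic chemotherapy, or radiation therapy, for malignancy.
- Exclusion 12: besides severe anemia, "Grade 1 white cell counts", defined by lymphocyte and neutrophil limits.
- Exclusion 13: positive serology for HIV, hepatitis B or hepatitis C.
- Exclusion 19: any condition that the investigator considers a threat to safety, communication or data quality.

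Inclusion 6 in section 7.1 also asks for a general medical condition that the investigator judges acceptable. Section 8.7.1 separately bars "Current treatment with immunosuppressive agents" before dosing.

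**The concern.** A safety exclusion protects participants only if it reaches the list that the site works through. Here the background section gives a categorical bar with its reason, and the working list does not repeat two of the four groups. A coordinator who follows sections 7.2, 9.1 and 9.3 correctly could enrol someone whom section 4.4.4 says is excluded.

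Safety and tolerability is the primary objective, and these exclusions are section 4.4.4's stated response to the latent-infection question. An ethics committee reading that section would take it that these people cannot enter. For the uncovered cases, entry depends on each investigator's opinion, so sites may differ. It is also unclear whether enrolling such a person would count as a protocol deviation under section 13.9, because the person could satisfy every criterion that does not rest on opinion.

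**Working it through.** No sample size, power or alpha figure is involved. The check takes each group in section 4.4.4 and looks for the criterion that carries it.

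1. **Current immunosuppressive agents: carried.** Exclusion 9 is limited to systemic or strong agents. Section 8.7.1 bars immunosuppressive agents without that limit, and exclusion 10 adds chemotherapy and radiation.
2. **History of immunosuppression: carried.** Exclusion 6 names past immunosuppressive therapy. As punctuated, the three-month limit belongs to systemic steroids, so the history clause has no time limit.
3. **Current autoimmune condition: carried in part.** No exclusion uses the term. Exclusion 5 bars a history, not only current disease, so in time it is wider than section 4.4.4. If inflammatory disease is read broadly, it reaches most autoimmune disease. Exclusions 6 and 9 catch patients who were or are treated with immunosuppressants. What remains is an autoimmune condition that a site would not class as inflammatory and that was never treated in that way. This part of the gap is thin.
4. **Documented immunodeficiency: carried in part.** Exclusion 13 covers HIV. Hepatitis B and C are infections, not immunodeficiencies. Exclusion 12 works as a laboratory proxy where lymphocytes or neutrophils are low. A documented antibody deficiency with both counts within limits, in a patient who never received immunosuppressive treatment, passes exclusions 5, 6, 9, 10, 12 and 13.

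For the patient in item 4, two criteria remain: inclusion 6 and exclusion 19. Both let an investigator refuse the patient, and neither requires it.

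The count is:
- groups named in section 4.4.4: 4
- carried by explicit criteria: 2 (items 1 and 2)
- carried in part: 2 (items 3 and 4)
- wholly absent: 4 − 2 − 2 = 0

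Of the 19 exclusions, none names autoimmune disease, and one contains the word immunodeficiency, as part of the name of the virus in exclusion 13. That word count shows where the list departs from section 4.4.4. It does not measure risk.

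**The case against.** The strongest reply is that section 4.4.4 is itself part of the protocol. Section 14.1 opens by requiring the investigator to follow the protocol as a whole, and section 13.9 defines a deviation as any variation from it, with breaches of the listed criteria as one example. On this view the bar already binds, and only the checklist is incomplete. Section 4.4.4 also tells investigators why impaired immunity matters here, which gives direction for using exclusion 19. The history prompt in section 9.1 already asks about immunosuppression and transplant.

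This softens the gap but does not close it. Every eligibility check points to the numbered criteria, and the section 9.1 prompt names neither autoimmune disease nor immunodeficiency and attaches no exclusion to what it collects.

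Other mitigation also stands. The masking of infection is presented as theoretical, and systemic IL-10 is expected to be low and short-lived. Hepatitis serology (exclusion 13) and the bar on current systemic antibiotics or antivirals (exclusion 15) deal with part of the infection question. Vital signs and adverse events are scheduled at every follow-up visit.

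A reader might go further and infer that only one of the four groups is properly carried, so that exclusion 6 must also be widened. The documents do not support this. Exclusion 6 is an explicit criterion for past immunosuppressive therapy. Counting it as a third gap requires either reading the three-month limit across the semicolon or requiring the phrase in section 4.4.4 to include causes other than treatment. Those non-drug cases largely overlap with immunodeficiency, so one gap would be counted twice.

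**Conclusion.** The inconsistency is real and narrow. Two of the four groups that section 4.4.4 says are excluded have no criterion of their own in section 7.2 or the synopsis and are only partly covered by neighbouring ones. The firm residue is documented non-HIV immunodeficiency with normal white-cell counts. The autoimmune residue is small and depends on how a site reads exclusion 5.

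This rests on three readings: that sites enrol from the numbered criteria, that the three-month limit in exclusion 6 applies to steroids only, and that inflammatory disease in exclusion 5 is read broadly. A narrower reading of exclusion 5 would widen the autoimmune part.

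How many of the roughly 270 planned participants could be affected cannot be estimated, and the documents do not show that anyone would be harmed. The ITT and Safety populations are defined by receipt of the injection or study drug, so no endpoint or analysis depends on this point. It is minor, but worth correcting because the exclusions are the sponsor's own and safety is the primary objective.

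**What to change.** Add two exclusions to section 7.2 and to the synopsis, in the sponsor's own terms: *current autoimmune condition* and *documented primary or acquired immunodeficiency*. Leave exclusion 6 as it is.

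The cost is a short protocol amendment and a slightly smaller eligible pool, by an amount the documents do not allow to be estimated. No visit, endpoint, sample size or analysis changes.

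If the sponsor did not intend a categorical bar, for example on mild autoimmune conditions, the sentence in section 4.4.4 could be narrowed to match the list. That would remove the contradiction but would exclude no additional patient, so adding the criteria is the better course.

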4.4.5 Possible Anticipated Adverse Events and Clinical Monitoring

Anticipated AEs for which there will be specific safety monitoring in humans will be based on the preclinical studies as well as the published reports of studies of IL-10 protein injections to healthy volunteers. Potential for local injection site infection is very low since aseptic technique will be used and the investigators are highly trained and experienced in the administration of intra-articular injections.

[figure not shown]
Based on published reports of IL-10 protein injections in humans, the following AEs could be attributed to XT-150-produced IL-10var. IL-10 protein doses were more than 1000-fold higher than can be expected with XT-150.

- Minor decreases in neutrophils and T-lymphocytes.
- Changes in hemoglobin, platelet counts, and leukopenia
- Flu-like adverse effects related to IL-10, including symptoms of headache, and fever, chills, nausea, and myalgias, as reported by Chernoff (1995), Huhn (1996, 1997), and van Deventer (1997).

None of these AEs have been recorded for any of the patients in clinical studies following knee injections with XT-150 doses up to 600 µg, including 0201 study participants who received a second injection in the 0203 study.

[figure not shown]
4.4.6 Risk-Benefit Summary

The IL-10var expressed by XT-150 is nearly identical to IL-10 that occurs naturally in the body. The targeted delivery of XT-150 directly to the joint space of the knee reduces potential systemic adverse effects since it primarily localizes in the synovial tissues with very low, transient expression levels of IL-10var in the circulation. Potential for local injection site infection is low since aseptic technique will be used and the investigators are highly trained and experienced in the administration of intra-articular injections.

Overall, based on risk/benefit analysis, the current study appears to be suitable for the planned population in this clinical trial.

